5.2 Pharmacology

The mechanism of clinical antitumor activity of Tarceva is not fully characterized. Tarceva inhibits the intracellular phosphorylation of tyrosine kinase associated with the epidermal growth factor receptor (EGFR).

Bioavailability of Tarceva following a 150mg oral dose is about 60% and peak plasma levels occur 4 hours after dosing. Food increases bioavailability substantially to almost 100%. Tarceva's half life is about 36 hours and it is cleared predominantly by CYP3A4 metabolism. Time to reach steady state plasma concentration is 7-8 days and no significant relationship has been observed of clearance to patient's age, body weight or gender. Smokers have a higher rate of Tarceva clearance than non-smokers. Tarceva is predominantly cleared by the liver. No data are currently available regarding the influence of hepatic dysfunction or hepatic metastases on the pharmacokinetics of Tarceva. Since Tarceva is predominantly metabolized by CYP3A4, inhibitors or inducers of CYP3A4 would be expected to increase and decrease exposure, respectively. A potential for drug-drug interaction exists when Tarceva is co-

administered with drugs that are highly protein bound or that are CYP3A4 and CYP1A2 inhibitors/inducers.

For patients who are being concomitantly treated with a potent CYP3A4 inhibitor, a dose reduction should be considered in the presence of severe adverse events. For patients who are being concomitantly treated with a potent CYP3A4 inducer, alternative treatments that lack potent CYP3A4-inducing properties should be considered.

Patients taking an enzyme-inducing anti-convulsant medication (phenytoin, carbamazepine, phenobarbital, Mysoline, Trileptal). It should be discontinued and converted to a nonenzyme-inducing anti-convulsant (Keppra, Depakote, Topamax, Lamictal or Neurontin) prior to the first dose of Tarceva.

In addition, altered coagulation parameters and bleeding have been reported in patients receiving Tarceva alone and in combination with other chemotherapeutic agents and concomitant warfarin-derivative anticoagulants. The mechanism for these alterations is still unknown. When warfarin is coadministered with Tarceva (anytime after Day 5), international normalized ratio (INR) and prothrombin time should be closely monitored (weekly until stabilized) and the anticoagulant dose should be adjusted as clinically indicated.

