5.3 Adverse Events/Precautions

The most common adverse reactions in patients receiving Tarceva monotherapy and in combination with chemotherapy are rash and diarrhea. Grade 3-4 rash and diarrhea occurred in 9% and 6%, respectively in Tarceva treated patients. Rash and diarrhea each resulted in study discontinuation in 1% of Tarceva treated patients. The median time to the onset of rash was 8 days and the median time to onset of diarrhea was 12 days.

There have been infrequent reports of ILD (interstitial lung disease) in patients receiving Tarceva for the treatment of NSCLC and other advanced solid tumors. In the randomized single agent study, the incidence of ILD (0.8%) was the same for both the placebo and Tarceva groups. The overall incidence of ILD from all studies was approximately 0.6%. If ILD is diagnosed, Tarceva should be discontinued and appropriate treatment instituted as necessary. There are no adequate and well controlled studies of Tarceva in pregnant women. Women of childbearing potential should be advised to avoid pregnancy while on Tarceva, and will need to practice birth control while on study, if premenopausal.

Asymptomatic increases in liver transaminases have been observed in patients on Tarceva; therefore, periodic liver function testing should be considered. Also, patients taking warfarin or other coumarin-derivative anti-coagulants should be monitored for

changes in prothrombin time or INR. NCI-CTC grade 3 conjunctivitis and keratitis have been reported infrequently in patients receiving Tarceva therapy. Corneal ulcerations may also occur.

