6.0 Study Methods

Study Calendar

Assessment	Screening	Baseline (1-3 days prior to day 1 of Tarceva)	Weekly During treatment	One Month Post RT (+/- 7 days)	Follow-up for patients on Tarceva (+/- 7 days)	Follow-up for patients off Tarceva (+/- 14 days)^{m,n,o}
-------------------	------------------	--	--	---	---	---

Histological confirmation of NSCLC	X					
CT/MRI of brain and report	X^b			X	X^m	X
CBC/Differential	X^b					
Platelet	X^b					
Complete Metabolic panel)	X^b					
Repeat sodium level			X^e			
CT or PET of Liver	X^c					
Medical History	X	X^d			X^{d,f}	X^d
Physical Examination	X^b		X	X	X^m	X
Concomitant Medications	X	X	X	X	X^{a,f}	
Serum Pregnancy test, if applicable	Xⁱ					

Assessment	Screening	Baseline (1-3 days prior to day 1 of Tarceva)	Weekly During treatment	One Month Post RT (+/- 7 days)	Follow-up for patients on Tarceva (+/- 7 days)	Follow-up for patients off Tarceva (+/- 14 days)^{m,n,o}
Document steroid dose		X	X	X		
Spitzer Quality of Life Index		X^k	X^l			
Folstein Mini-Mental Status Exam		X^k	X^l			
Optional neurocognitive tests ^p		X^k				
Consent for EGFR expression testing (Optional)	X					
Informed Consent	X					
Vital Signs		X		X	X^m	X
Adverse Event Check ^g			X	X	X^f	X
PT/INR if patient on Coumadin	X		X^{h,j}	X^h	X^h	X

a = until 30 days after last dose of Tarceva

b = within 30 days of starting treatment

c = within 3 months of starting treatment

d = update only

e = Patient will have repeat sodium on RT day 7 and RT day 14 if baseline sodium \leq 135 mg/dl

f= Patients will be seen by the research nurse monthly while on Tarceva (+/- 7 days), and/or one month post last dose of Tarceva (+/- 7 days). Patients on Tarceva, who are unable to return for their follow up visits and 1 month post last dose of Tarceva visit, will be contacted by the research nurse by phone to review/asses the following; Update of medical history, assessment of AE's concurrent medications. They will return their unused Tarceva medication along with their medication diaries to the research nurse via mail.

- g= All adverse events will be collected until 30 days after the last study dose of Tarceva or 30 days post RT visit (whichever is last), then only neurocognitive decline will be captured.
- h = Only if patient has abnormal values during initial screening testing
- i= within 7 days of starting protocol treatment
- j= weekly until stable
- k= Prior to radiation
- l = During last week of radiation therapy (+/- 7 days)

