6.1 Concomitant Medications

The Investigator will be permitted to prescribe treatment(s) at his or her discretion, which must be recorded on the Case Report Form (CRF). All concomitant meds will be tracked until 1 month post last dose of Tarceva.

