6.4 Dose Modification / Toxicity Management

Anti-diarrheal and anti-rash medications may be introduced if clinically indicated. Previous Phase I and II studies have demonstrated the frequency and severity of diarrhea can be managed with loperamide. The recommended dose of loperamide is 4 mg at first onset, followed by 2 mg every 2 to 4 hours until diarrhea resolves for 12 hours.

Skin rash or dermatosis has been observed during the first several days of treatment with Tarceva in many patients and has been noted to diminish in severity despite continued treatment. No controlled clinical trials have been conducted to allow definitive recommendations on the treatment of Tarceva -related rash.

Patients who develop a rash characterized by pustules or raised red areas may be treated with oral minocycline (100 mg BID for 7 – 10 days to a maximum of 150 mg BID for 7 – 10 days as clinically indicated) at the discretion of the Investigator. Minocycline is known to interfere with anticoagulants and oral contraceptives. Patients treated with minocycline who are taking anticoagulants and/or oral contraceptives will be instructed to use a second barrier contraceptive while on Minocycline and should be monitored accordingly.

Dose adjustments may be made for toxicity and are to be made based on the greatest degree of toxicity. The initial dose reduction is from 150 mg/day to 100 mg/day. If significant toxicity is still apparent, the dose may be reduced a second time to 50 mg/day. Significant toxicity will be defined as any grade 3 or 4 toxicity that the patient find unbearable. Any patient who fails to tolerate treatment of 50 mg/day will be allowed to have a drug holiday for up to 7 days. Any patient requiring a treatment break longer than seven days may be withdrawn from the study based on the discretion of the principal investigator. Patients may resume drug or increase a previously decrease dosage based on the discretion of their medical oncologist. For analysis and monitoring patients on any dose of drug will be considered “on active treatment”.

Tarceva dosing should be discontinued for any grade 3 or greater toxicity that does not respond to treatment or failure to recover from hematological toxicity within 14 days.

For patients that are off Tarceva for more than 30 days the only toxicities that will be reported and recorded in PDMS will be neurocognitive decline.

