8.0 Adverse Events

All adverse events will be graded according to NCI CTC version 3.0

Adverse drug experience means any adverse event associated with the use of a drug in humans, whether or not considered drug related, including the following: an adverse event occurring in the course of the use of a drug product in professional practice; an adverse event occurring from drug overdose, whether accidental or intentional; an adverse event occurring from drug abuse; an adverse event occurring from drug withdrawal; and any failure of expected pharmacological action (21 CFR 314.80).

An adverse event is any adverse change from the subject's baseline condition, including any clinically significant laboratory test value abnormality that occurs during the course of the clinical study after the informed consent is signed, whether the adverse event is considered related to the treatment or not.

All adverse events will be collected until one month post last day of Tarceva or radiation (whichever is last). This may require obtaining clinical blood samples for appropriate laboratory tests until their values return to baseline levels or performing follow-up physical examinations until resolution of identified abnormalities.

The most common adverse reactions in patients receiving single-agent TARCEVA 150 mg were rash and diarrhea. Grade 3/4 rash and diarrhea occurred in 9% and 6%, respectively, in TARCEVA-treated patients. Rash and diarrhea each resulted in study discontinuation in 1% of TARCEVA-treated patients. Six percent and 1% of patients needed dose reduction for rash and diarrhea, respectively. The median time to onset of rash was 8 days, and the median time to onset of diarrhea was 12 days.

	TARCEVA 150 mg N = 485			Placebo N = 242		
NCI CTC Grade	Any Grade	Grade 3	Grade 4	Any Grade	Grade 3	Grade 4
MedDRA Preferred Term	%	%	%	%	%	%
Rash	75	8	<1	17	0	0
Diarrhea	54	6	<1	18	<1	0
Anorexia	52	8	1	38	5	<1
Fatigue	52	14	4	45	16	4
Dyspnea	41	17	11	35	15	11
Cough	33	4	0	29	2	0
Nausea	33	3	0	24	2	0
Infection	24	4	0	15	2	0
Vomiting	23	2	<1	19	2	0
Stomatitis	17	<1	0	3	0	0
Pruritus	13	<1	0	5	0	0
Dry skin	12	0	0	4	0	0
Conjunctivitis	12	<1	0	2	<1	0
Keratoconjunctivitis sicca	12	0	0	3	0	0
Abdominal pain	11	2	<1	7	1	<1

Rare, But Serious

In some patients taking erlotinib and oral blood thinners INR have been reported abnormally elevated. The elevation of INR was associated with bleeding.

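### Study Calendar footnote h makes PT/INR checks during Tarceva depend on an abnormal screening value, which conflicts with sections 5.2 and 5.3 and leaves out patients who start warfarin after screening

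*Combined protocol and SAP*

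**What the plan says.** The calendar row is labelled "PT/INR if patient on Coumadin". It has five marked cells: screening, weekly during treatment, one month post RT, follow-up on Tarceva, and follow-up off Tarceva. Three of them (weekly, one month post RT, on Tarceva) carry the footnote "h = Only if patient has abnormal values during initial screening testing". The weekly cell also carries "j= weekly until stable".

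Section 5.2 states: "When warfarin is coadministered with Tarceva (anytime after Day 5), international normalized ratio (INR) and prothrombin time should be closely monitored (weekly until stabilized"). Section 5.3 says that "patients taking warfarin or other coumarin-derivative anti-coagulants should be monitored for" changes in prothrombin time or INR. Neither section refers to a screening result.

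Warfarin is not among the exclusions in section 4.2, and section 6.1 leaves concomitant treatment open: "The Investigator will be permitted to prescribe treatment(s) at his or her discretion".

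**The concern.** The screening value is taken before Tarceva, so it cannot show an interaction that arises once the two drugs are taken together. It is the wrong trigger for a test meant to detect that interaction. It also cannot work for someone who begins warfarin later, because the row asks for a screening PT/INR only from patients already on Coumadin.

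A later start is foreseeable. Besides the freedom given by section 6.1, section 8.0 lists blood clots among the rare but serious effects of erlotinib.

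What is at stake is patient safety. Section 8.0 says of erlotinib taken with oral anticoagulants: "The elevation of INR was associated with bleeding". All patients in this trial have brain metastases. The calendar offers no other routine laboratory signal during treatment: blood counts, platelets and the metabolic panel are marked at screening only, and the one repeat blood test is a conditional sodium level. Adverse event checks would record a bleed, but only after it happened.

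**Working it through.** No alpha, power or event count is involved. The check is to read the PT/INR row cell by cell against the text and then follow two kinds of patient through it.

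**The row (section 6.0)**

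| Column | Mark | Limit |
|---|---|---|
| Screening | X | row label only |
| Baseline | blank | – |
| Weekly during treatment | X | h, j |
| One month post RT | X | h |
| Follow-up on Tarceva | X | h |
| Follow-up off Tarceva | X | no h; column header carries m, n and o |

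Footnote h is on 3 of the 5 marked cells. Those 3 are all the post-baseline columns that can fall during Tarceva. Footnote j is on 1 of the 3; it sets a frequency and does not lift h in the same cell.

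**Patient who starts warfarin after screening**

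1. Not on Coumadin at screening, so the row calls for no screening PT/INR.
2. With no screening value under the row, h is not met in any of the three columns: 0 of 3 call for a check.
3. The concomitant-medication row would record the new warfarin, but no test is tied to that entry.
4. Section 5.2 would have the same patient tested once a week until stable. The documents give no time to stability. If it took an assumed 2, 4 or 6 weeks, that would be 2, 4 or 6 checks, so the count simply follows the assumption.

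**Patient on warfarin at screening**

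1. If the screening value is abnormal, h is met and the marked checks apply.
2. If it counts as normal, h fails and 0 checks are called for in the three columns.
3. Without h, the grid would give the following through the one-month visit. Fourteen fractions at five per week (section 7.0) span 18 calendar days from a Monday or Tuesday start and 20 from a later weekday, with no holidays. Adding the minimum 6-day lead-in (section 5.6): 18 + 6 = 24 to 20 + 6 = 26 days. If the weekly column starts with Tarceva, checks fall on days 7, 14 and 21: at most 3, or 1 if the first is stable. Adding the one-month visit: 1 + 1 = 2 to 3 + 1 = 4.
4. Four is not a ceiling, because the lead-in is only a minimum. An assumed 10-day lead-in gives 28 to 30 days, a fourth weekly check on day 28, and 4 + 1 = 5.

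These figures count calendar entries. They are not tests known to be lost.

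**The case against.** The strongest reply is that the protocol already covers the later starter. Section 5.2 applies at any time after Day 5, which includes warfarin begun mid-study, and no text says that the calendar overrides it. Section 6.4 adds that anticoagulated patients given minocycline "while on Minocycline and should be monitored accordingly". Footnote h does not forbid a test. This stands: a reader might infer that no monitoring is planned for these patients, and the documents do not support that. The gap is in the grid only. It still matters, because section 6.2 sends monitoring and follow-up to the calendar. For patients living abroad, who receive a 90-day supply under a home physician, section 5.6 lists the consent, abstract, schema and on-treatment evaluations as the papers to be sent, not the full protocol. Whether those papers repeat 5.2 cannot be seen.

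Second, warfarin is given to prolong PT/INR, so most established users would have an abnormal value and meet h. This also largely stands, although the protocol does not define abnormal for anticoagulated patients. It does nothing for later starters.

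Third, a reader might infer that testing is conditional while the interacting drug is taken and unconditional afterwards. That is too strong. The off-Tarceva cell lacks h, but footnote n in its column header allows telephone follow-up for deteriorating patients, and footnote o limits recording to survival after CNS progression. Likewise, the one-month post-RT visit is not always on drug, since section 6.2 lets patients stop Tarceva at any time.

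**Conclusion.** The conflict is real and can be read directly from the text: the calendar sets a screening condition that 5.2 and 5.3 do not. Its firm size is 0 of 3 calendar columns for a patient who starts warfarin on Tarceva after screening, and likewise for a warfarin user whose screening value counts as normal, probably a small group.

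The number of patients affected cannot be derived, since the documents give no rate of warfarin use. Nor can the number of tests actually lost, because sites that follow 5.2 and 5.3 would test anyway. The counts above depend on the assumed time to stability and length of lead-in.

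The primary survival analysis is unaffected, and adverse event and SAE reporting would still record clinical bleeding. This is a safety-schedule inconsistency that should be corrected because it is cheap to correct. It is not evidence that patients went unmonitored.

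**What to change.** Replace footnote h with: *for any patient taking warfarin or another coumarin derivative with Tarceva, including if started after screening: weekly until stable, per 5.2, then as clinically indicated; patients with abnormal screening values keep the visit checks marked in this row.* Attach footnote j to the on-Tarceva follow-up cell as well, so that warfarin begun during later follow-up is covered. The row label names only Coumadin and should be widened to match.

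Simply deleting h is less good. It would make the visit checks open-ended for as long as Tarceva continues, at a frequency the cell does not define (it carries neither f nor m), and 5.2 asks only for checks until values stabilize.

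The cost is a footnote edit and the routine blood draws that 5.2 already calls for. Some would have to be taken locally, for patients followed by phone or living abroad.

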3.0 Study Design

Twenty patients will be collected from this M.D. Anderson based study and the data will be combined with an identical 20 patient study that [name] started while at the Arizona Cancer Center. The Arizona study has enrolled 15 of the planned 20 patients (as of August 2008), and by combining these two studies we will have a total of 40 patients for final analysis.

Study Schema

Patients must have radiographic evidence of brain metastases, proven with CT or MRI so that we can stratify patients by the number of brain metastases. Additionally, they must have no prior history of cranial radiation (other than stereotactic radiosurgery). Once enrolled, patients will receive Tarceva (150mg PO QD) for at least 6 days prior to starting and during whole brain radiotherapy (WBRT). External beam radiation will consist of opposed laterals to a total dose of 3500cGy in 14 daily fractions.

Upon completion of external whole brain radiation, patients will continue taking Tarceva (150mg PO QD) until documentation of disease progression (unless treating physician feels that stopping Tarceva would adversely affect the patient) or if patients are unable to tolerate study drug due to toxicities. Patients will be allowed to stop taking Tarceva at any time during this trial. Following completion of WBRT patients will have a repeat MRI or CT at 1 month after completion of WBRT, and then at 3 month intervals, or sooner if indicated by symptom progression. Additionally, during active treatment period of this trial, patients will not be allowed to have surgical debulking of CNS tumors, or stereotactic radiosurgery of CNS lesions, as this need would correlate with progression of disease. Patients will be allowed to receive palliative radiation if needed to address symptoms. Patients will be allowed to dose reduce down to 50mg per day, and may also take a treatment break of up to seven days.

Survival will be compared to a database of patients with similar histologies and stratified according to their Recursive Partitioning Analysis (RPA) class and the number of brain metastases, at time of diagnosis (16). The RPA is a predictive tool used to estimate survival based on age, performance status, and presence of extracranial metastasis.

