5.6 Administration

Patients will receive only a 30-day supply of drug at a time, from the Investigational Pharmacy. The patient will be seen by the nurse once approximately every 30 days (+/- 7 days) to review number of pills taken during the previous 30 days (+/- 7 days), and to receive another 30 days of medication. If patients are unable to return for their follow up visits, we will review their mediations and current drug logs over the phone and their Tarceva refills will be mailed to them via the investigational pharmacy.

Patients will begin taking Tarceva at least 6 days before their first dose of radiation, daily during radiation therapy, and then daily until progression is documented (unless treating physician feels that stopping Tarceva would adversely affect the patient), adverse events warrant discontinuation or the patient decides to stop taking the medication.

Tarceva tablets should be taken once daily. Each Tarceva dose is to be taken with up to 200 mL (~ 1 cup or 8 oz) of water, and should be taken 1 hour before or 2 hours after meals or medications, including grapefruit juice, vitamins, and iron supplements.

For patients residing outside the U.S: Patients will receive a 90 day supply of Tarceva at a time, from the Investigational Pharmacy; The study PI will have physician-to-physician communication regarding protocol enrollment; a letter (Appendix G) will be sent to the home physician outlining the subject's participation and requesting the home physician agreement to supervise the subjects care. The home physician will be requested to provide any patient medication diaries, progress notes, hospitalization records, toxicities, tests, and procedures to the study PI or his research staff at MD Anderson within 48 hours. The home physician will be asked that any questions related to the study drug dosing, schedule, or side effects be directed to study PI. All life

threatening clinical events must be reported by the home physician to the study PI within 24 hours of documented occurrence. The home physician will be provided with study contact numbers for business and non-business hours.

Protocol required evaluations outside MDACC will be documented by telephone, fax or e-mail. Fax and/or e-mail will be dated and signed by the MDACC physician, indicating that they have reviewed it.

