- m= every 3 months (+/- 14 days) for 2 years then every 6 months after
- n= patients with deteriorating conditions who are unable to return may be followed up by telephone. MRI brain, physical exam, mini-mental exam, QOL Index and neurocognitive testing may be excluded.
- o= for patients with progressive CNS disease we will record survival only.
- p= Optional neurocognitive tests will include Digit Span, Digit Symbol, Hopkins Verbal Learning Test, Controlled Oral Word Association, Trail Making Test Part A, Trail Making Test Part B, Grooved Pegboard, Barthel [name]. Anderson Symptom Inventory, and Functional Assessment of Cancer Therapy with Brain Module. As of July 18, 2012- Optional tests will no longer be completed.

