11.5.1 Endpoint Analysis

11.5.1.1 Survival

We will use the product limit estimator of Kaplan and Meier (1958) to estimate the overall survival of all patients using the intent-to-treat principle. We will report the median survival and its associated 95% confidence interval.

We will also estimate overall survival stratified by treating institution and class, as described above in section 11.2.

We will compare the estimates of survival from this study with a recent reported phase III randomized RTOG trial, 0118, which randomized 332 patients to WBRT with or without Thalidomide (19). Our patients will be compared to both the overall survival and CNS progression free survival from this study.

We will tabulate cause of death by treating institution and by class, and we will compare the cause of death for patients in this study with patients from RTOG 01188.

We will analyze progression-free survival (PFS) in the same manner as overall survival.

We will use the methods described in Klein and Moeschberger (1997) to test for differences in survival between the matched pairs. To help us understand how similar/dissimilar patients from MDACC and Arizona are we will summarize the demographic and clinical characteristics of these patients separately. We will also estimate the survival of the 40 patients (20 from MDACC and 20 from AZCC) with the product-limit estimator of Kaplan and Meier (1958) stratified by study center (MDACC, AZCC), and we will use Cox (1972) proportional hazards regression to model survival of these 40 patients as a function of study center and estimate the hazard ratio (MDACC:AZCC) with a 95% confidence interval. For the match control based variables we will use patients from a prior randomized whole brain radiation therapy (WBRT) study performed by the Radiation Therapy Oncology Group (RTOG) study (RTOG 0118). Patients will be matched based on age, KPS, number of brain metastasis and control of systemic disease. If there is more than one match available for a patient we will review all cases.

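### Off Tarceva, patients who deteriorate and cannot return may skip the brain scan, and section 11.5.1.1 has no rule for dating progression without one

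*Combined protocol and SAP*

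**What the plan says.** **Off Tarceva.** In the section 6.0 calendar, the header of the off-Tarceva follow-up column carries markers m, n and o. Footnote m sets visits "every 3 months (+/- 14 days) for 2 years then every 6 months after". Footnote n then allows that "patients with deteriorating conditions who are unable to return may be followed up by telephone", and adds that "MRI brain, physical exam, mini-mental exam, QOL Index and neurocognitive testing may be excluded". Footnote o limits data to survival once CNS disease has progressed. The medical-history update and adverse-event check stay in that column and are not among footnote n's exclusions. Footnote g keeps neurocognitive decline as the one event still captured after the 30-day window.

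**On Tarceva.** The CT/MRI and physical-examination cells carry only footnote m, so 3-monthly imaging stays required. Footnote f lets the monthly nurse review of history, adverse events and medications be done by telephone. Under 5.6, for patients unable to return, "we will review their mediations and current drug logs over the phone and their Tarceva refills will be mailed to them". Tarceva is taken "daily until progression is documented", with an exception at the treating physician's judgement (3.0, 5.6, 6.2).

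**Imaging and analysis.** Section 3.0 plans a scan 1 month after radiation, "then at 3 month intervals, or sooner if indicated by symptom progression". Time to progression is secondary objective 2.2.3. Section 11.5.1.1 says "We will analyze progression-free survival (PFS) in the same manner as overall survival" and sets the result beside the CNS PFS of RTOG 0118. The documents give no progression criteria, no rule for clinical progression without a scan, and no censoring rule for missed scans.

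**The concern.** What triggers the omission of the scan is deterioration, and in a brain-metastasis trial deterioration is a likely sign of the event being measured. The missing assessment therefore depends on the outcome, and a scan not done cannot be recovered at analysis. Section 3.0 wants imaging sooner when symptoms progress, while footnote n excuses it for some of the same patients.

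Telephone contact may still record neurological decline, but nothing says whether that counts as progression. If it does not, such a patient either stays progression-free until death or is censored at the last clear scan. Both choices tend to lengthen PFS or time to progression. The trial has no concurrent arm in which the same distortion could cancel.

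**Working it through.** **1. Who is exposed.** Footnote n covers off-Tarceva follow-up only. A patient who stopped Tarceva at documented CNS progression already has the event, and footnote o then asks for survival alone. The exposed patients stopped Tarceva before documented CNS progression (6.2 allows stopping at any time), later deteriorated, could not return, and had the optional waiver applied. The documents do not give their number.

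**2. The plan's own figure.** The only powered calculation is for overall survival (11.3): 40 patients, median 4.2 against 6.0 months, one-sided 0.10, 24 months of accrual plus 9 of follow-up.
- Probability of death at median 6.0, with λ = ln2/6: 1 − [exp(−9λ) − exp(−33λ)]/(24λ) = 0.880, so 40 × 0.880 = 35.2 deaths.
- Power = Φ(√35.2 × ln(6.0/4.2) − 1.282) = Φ(2.117 − 1.282) = 0.798.

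The stated 80% is reproduced. Vital status can be obtained by telephone, so footnote n does not touch this result.

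**3. Missed progression dated at death, short survival afterwards.** Assumptions not in the documents: exponential progression with median 3 or 4 months; 15%, 25% or 40% of progressions unscanned; death 1, 1.5 or 2 months later; scheduled scans at months 2, 5, 8 and so on. A missed patient is wrongly counted progression-free at 6 months only if progression fell after month 6 − d (d = months from progression to death) but before the month-5 scan that would have found it.
- Median 3, d = 2, 40% missed: 0.40 × (2^(−4/3) − 2^(−5/3)) = 0.40 × (0.397 − 0.315) = 3.3 points.
- Median 4, d = 2, 40% missed: 0.40 × (0.500 − 0.420) = 3.2 points.
- d = 1: the interval is empty, so 0 points.

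Across all 18 combinations, simulation gives a rise of 0 to 3.3 points in six-month PFS and a shift of 0.0 in the median. If symptoms would otherwise have triggered an immediate scan, the interval runs from 6 − d to 6, and the largest case becomes 0.40 × (0.397 − 0.250) = 5.9 points.

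**4. Longer survival afterwards, both conventions.** Simulation on further assumptions: median survival after progression 2 to 3 months; death without progression at 10% of the progression hazard; scans at 1.9 months and then every 3. Six-month PFS with full scanning is 27% to 38%.

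| Progressions unscanned | Rise in six-month PFS (dated at death, or censored at last scan) |
|---|---|
| 10% | about 2 to 3 points |
| 20% | about 3 to 6 points |
| 30% | about 5 to 9 points |

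The sampling standard error at 40 patients is √(0.27 × 0.73/40) = 7.0 to √(0.38 × 0.62/40) = 7.7 points. Both checks spread the missed share over all progressions, whereas only the narrower group in step 1 is exposed.

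**The case against.** The exposed group may be small, the waiver is optional, and the telephone contact is not empty: history, adverse events and neurocognitive decline are still collected. If reported decline were counted as progression, the upward bias would shrink or vanish. Scanned patients are themselves dated on a 3-monthly grid, so a death soon after an unseen progression often comes before the next scheduled scan. Because PFS counts death, censoring at the last scan is mainly a matter for time to progression. All of this stands, and it limits the size. It does not supply the missing rule.

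Three stronger readings are tempting and are not supported:
- A reader might infer that mailed refills disable stopping at progression. Footnote n does not reach the on-Tarceva column, 3-monthly and symptom-triggered imaging stay in force there, and continuing after progression is already discretionary. All that can be said is that a refill is not tied to a current scan.
- A reader might infer that refills are mailed because patients are too ill. Section 5.6 and footnote f say only that they are unable to return.
- A reader might infer a proven advantage over RTOG 0118. That trial's scan schedule and handling of missed scans are not in the documents.

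**Conclusion.** The concern holds for off-Tarceva follow-up. Footnote n creates informative missing scans, and 11.5.1.1 does not say how decline without a scan is dated or censored. The likely direction is upward for PFS and time to progression, provided the event is dated at death or the patient is censored at the last scan; the plan states neither convention. The size cannot be derived from the documents. On the assumed inputs it is probably modest for PFS and within one to two sampling standard errors at 40 patients, but it is systematic, so more patients would not remove it. Only secondary endpoints are affected; primary overall survival and its 80% power are not. The refill question is separate and is one of passages to reconcile.

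**What to change.** In footnote n and section 11.5.1.1:
- **(a)** Accept local brain imaging reports for any patient unable to return, by the telephone, fax or e-mail route in 5.6. State that this covers patients within the U.S., because that text follows the paragraph on patients living abroad.
- **(b)** Record the reason for each missed scan. Use the telephone contact and the neurocognitive-decline capture in footnote g to date a clinical CNS progression event when neurological decline is reported, no scan is obtained and no other cause is documented.
- **(c)** Report radiographic-only PFS as a sensitivity analysis.

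Separately, the sponsor should reconcile mailed refills (5.6, footnote f) with the imaging still required on Tarceva and with the text on stopping at documented progression (3.0, 5.6). No clinical rule is proposed here.

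The cost is a few sentences, an added question in the telephone contact and one extra analysis. The downside is that some non-CNS decline will be counted as CNS progression, so reported PFS may be slightly shorter.
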